14.0 Body Fluid Biospecimens

14.1 Summary Table of Research Blood and Body Fluid Specimens to be collected for this Protocol

Correlative Study (Section for more information)	Mandatory or Optional	Blood or Body Fluid being Collected	Type of Collection Tube (color of tube top)	Volume to collect per tube (# of tubes to be collected)	Baseline	Day 1 of Cycle 2 and 3	Process at site? (Yes or No)	Temperature Conditions for Storage /Shipping
Correlative Studies	Mandatory	Blood	2 purple top tubes	Volume of 7cc	X		Yes	Frozen at -80 centigrade, Shipped frozen
Correlative Studies*	Optional	Blood	2 purple top tubes	Volume of 7cc		X	Yes	Frozen at -80 centigrade, Shipped frozen

*If the patient does not participate in the optional blood draws, it does not cause the patient to be ineligible; however, the collection of the blood is **strongly recommended**.

14.2 Collection and Processing

14.21 Correlative Research

This protocol will check the following laboratory-based translational studies from the blood at baseline and at the time of completion of the intervention:

1. Biomarkers to explore convalescence will be examined. Biomarkers associated with bacterial translocation, enterocyte damage and intestinal epithelial barrier function will be measured with and without lipopolysaccharide (LPS) stimulation in vitro. LPS binding protein (LBP), bactericidal/permeability increasing protein (BPI), soluble CD14 (sCD14), 16s rDNA, intestinal fatty acid binding protein (I-FABP) and zonulin in plasma will be measured in this manner.
2. We will also measure plasma CRP and d dimer. Commercially available enzyme-linked immunosorbent assays will be used according to the manufacturer's instructions for measuring for inflammation-coagulation parameters.
3. Plasma cytokines involved in the pro-inflammatory cascade will be assessed. These cytokines include TNF- α , IFN- γ , IL 1, IL 6, IL 10, as well as neopterin. Standard enzyme-linked immunosorbent assay kits will be used according to manufacturer's recommendations.

For the translational component of this study, patients will have blood drawn at the time points specified in section 4.0.

Blood will be drawn in 2 purple top tubes capable of holding a blood volume of 7cc. Each tube will be spun down, and the plasma will be stored at -80 degrees centigrade.

Frozen plasma will be batched and sent to EnterHealth at the end of the study (see below for shipping details.) ELISA kits will be used to assay all the proteins.

14.3 Shipping and Handling

14.31 Kits will be used for this study.

14.311 Kits will be supplied by the Biospecimen Accessioning and Processing Shared Resource (BAP).

14.312 The kit contains supplies and instructions for collecting, processing and shipping specimens.

14.313 Participating institutions may obtain kits by faxing the Supply Order Form to the number listed on the form. Because we are charged for all

outgoing kits, a small, but sufficient, supply of the specimen collection kits should be ordered prior to patient entry. Supply Order Forms must be filled in completely and legibly for quick processing.

- 14.314 Kits will be sent via Fed Ex® Ground at no additional cost to the participating institutions. Allow at least two weeks to receive the kits.
- 14.315 Kits will not be sent via rush delivery service unless the participating institution provides their own Fed Ex® account number or alternate billing number for express mail. Cost for rush delivery of kits will not be covered by the study.
- 14.316 All specimens **must be collected and shipped Monday – Thursday ONLY.**

15.0 Product Information

- 15.1 Serum-Derived Bovine Immunoglobulin Protein Isolate (SBI, EnteriaGam™) or matching placebo

- 15.11 **Background:** Serum-derived bovine immunoglobulin protein isolate is an orally administered prescription medical food containing a proprietary formulation of bovine immunoglobulin (> 50% IgG) and other serum proteins. The product is manufactured in accordance with Good Manufacturing Practices and FDA guidelines for medical food ingredients.

It is indicated for the nutritional management of a patient with enteropathy who, because of therapeutic or chronic medical needs, has limited or impaired capacity to ingest, digest, absorb, or metabolize ordinary foodstuffs or certain nutrients.

Serum-derived bovine immunoglobulin protein isolate must be non-digestible and able to reach the gastrointestinal tract to benefit an immunocompromised or otherwise dysfunctional GI mucosa. In humans, SBI is used as a passive, immunity-enhancing nutrient to augment traditional medications. Clinical studies have provided evidence that SBI lowers total and LDL cholesterol in patients with mild hypercholesterolemia, reduces symptoms of gastroenteropathy in IBS-D and HIV+ patients, increases GI absorption, and decreases GI permeability.

15.12 **Formulation:** Serum-derived bovine immunoglobulin protein isolate is a light-colored powder composed of finely ground flakes of immunoglobulin and other serum proteins (ie, transferrin, albumin, alpha and beta proteins). Serum-derived bovine immunoglobulin protein isolate is supplied in individual packets containing 5 grams of SBI and the following ingredients: dextrose, orange (natural and artificial flavors) and coloring (Yellow #6). Matching placebo packets will be supplied and will appear identical to SBI with respect to volume, appearance, and taste. The ingredients of the placebo will include dextrose, orange (natural and artificial flavors) and coloring (Yellow #6).

15.13 **Preparation and storage:** Blinded investigational product (SBI or matching placebo) will be packaged in kits containing 5 grams of SBI per each packet or as matching placebo packets. An investigational product kit with a unique ID number will contain 14 packets (7 days of required product) and 4 extra packets (18 packets total) to accommodate the flexibility with return visits. Packets are to be stored at 20-25°C (68-77°F), with excursions permitted between 15-30°C (59-86°F).

15.14 **Administration:** SBI is administered orally or enterally. Each patient will be instructed to add the contents of one packet (5 grams) to a cup and dissolve the powder with approximately on-half cup (4 fl. ounces or 120 mL) of water. The patient will stir to mix and drink the contents. The patient will take one dose twice a day, in the morning and the evening, with or without food. Foods such as applesauce or pudding may be used instead of liquid to blend the product if the patient desires.

15.15 **Potential Agent Interactions:** No significant interactions of SBI with commonly prescribed medications have been observed.

15.16 **Known potential toxicities:** Study subjects with known beef allergies or allergies to other components of SBI should not take SBI. As with any ingested food or product, subjects who develop a hypersensitivity or food intolerance to SBI should discontinue its use. Subjects who are pregnant or breastfeeding should not take SBI, as there are no data regarding the effects. Serum-derived bovine immunoglobulin has self-affirmed generally recognized as safe (GRAS) status, with no objections from the FDA, and is demonstrated to be safe and well tolerated in pediatric and adult patients. SBI is marketed in Mexico, the Czech Republic, Japan, Egypt, and the United States. More than 100,000 kg of SBI in various dosages have been ingested by the general population since 2001. No serious adverse events have been reported to the manufacturer or the FDA. Literature reports indicate AEs include worsening or reoccurrence of diarrhea, constipation, and worsening neuropathy. Increased urination, stomach cramps, fatigue, headache, sore throat, softened stools, and nausea have also been reported.

15.18 Agent procurement:

Serum-derived bovine immunoglobulin protein isolate and matching placebo will be manufactured by Proliant Biologicals, Boone, Iowa in accordance with Good Manufacturing Practice (GMP) and FDA guidelines for medical good ingredients (21 CFR Part 110) and will be provided by Entera Health Inc.

15.19 Nursing Guidelines:

- 15.191 Due to the early investigational nature of this medical food, not all side effects can be known at this time. Assess for side effects and monitor patients closely.
- 15.192 Patients with beef allergy or intolerance should not take SBI.
- 15.193 GI adverse events may occur. Treat symptomatically and monitor for effectiveness.
- 15.194 Warn of possibility of neuropathy. Instruct patients to report any development or increase in neuropathy to the study team.
- 15.195 Headache may occur. Treat symptomatically and monitor for effectiveness.

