3.0 Patient Eligibility

3.1 Inclusion Criteria

- 3.11 Age \geq 18 years.
- 3.12 Diagnosis of gynecological cancer of any type or strong suspicion for cancer.
- 3.13 Patients must have begun postoperative oral intake of food prior to registration.
- 3.14 Open laparotomy or laparoscopic surgery undertaken with cancer therapeutic intent (not a subsequent surgery to manage a postoperative complication) that had occurred \leq 7 days prior to registration and that entailed more than a simple hysterectomy.
- 3.15 The following laboratory values obtained \leq 21 days prior to registration.
 - Creatinine \leq 1.5 x the upper limit of normal (ULN)
 - Absolute neutrophil count \geq 1500/mm³
 - Platelet count \geq 100,000/mm³
- 3.16 Ability to complete questionnaire(s) by themselves or with assistance.
- 3.17 Provide informed written consent.
- 3.18 Negative (serum) pregnancy test done \leq 7 days prior to randomization, for women of childbearing potential only.
- 3.19 Willing to provide mandatory baseline blood samples for correlative research purposes (see Section 6.12 and 14.0).

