4.0 Test Schedule

Tests and procedures	Active Monitoring Phase				Observation/crossover (ends after 16 weeks of total study participation)
	≤21 days prior to randomization	Day 1 of Cycle 2 and 3 (+/- 3 days)	Weekly from registration for 12 weeks total	At the end of intervention (+/- 3 days)	
Patient assessment (includes weight**)	X				
Adverse event assessment	X	X**		X**	X**
Pregnancy test ¹ (Serum)	X				
Hematology group					
HgB					
WBC	X				
PLT					
ANC					
Chemistry group					
Creatinine	X				
Patient Questionnaire					
Booklets ² , (Appendix 2-5)	X		X	X	X
Blood specimens (see Section 14.0) ^{3,R}	X	X*			

1. For women of childbearing potential only. Must be done ≤7 days prior to registration.
2. Patient questionnaire booklets **must** be used; copies are not acceptable for this submission. Patients are required to fill out the questionnaires at baseline, and weekly for the duration of study participation, (16 weeks total, includes patients who never started therapy).
3. Blood specimens will be collected and submitted at baseline. Kits are required. Baseline blood specimen is to be collected after consent and prior to patient receiving study agent.

R Research funded (see Section 19.0)

*These blood draws are optional but strongly recommended.

** If patient cannot return, this assessment can be done by phone by the study coordinator (includes patient reported weight). However, study questionnaires must be mailed back.

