In addition to submitting initial IRB approval documents, ongoing IRB approval documentation must be on file (no less than annually) at the Registration Office ([contact]). If the necessary documentation is not submitted in advance of attempting patient registration, the registration will not be accepted and the patient may not be enrolled in the protocol until the situation is resolved.

When the study has been permanently closed to patient enrollment, submission of annual IRB approvals to the Registration Office is no longer necessary.

6.14 Prior to accepting the registration, the registration/randomization application will verify the following:

- IRB approval at the registering institution
- Patient eligibility
- Existence of a signed consent form
- Existence of a signed authorization for use and disclosure of protected health information

6.15 Intervention on this protocol must commence at Mayo Clinic Rochester, under the supervision of a medical oncologist.

6.16 Intervention cannot begin prior to registration and must begin \leq 7 days after registration.

6.17 Pre-intervention tests/procedures (see Section 4.0) must be completed within the guidelines specified on the test schedule.

6.18 All required baseline symptoms (see Section 10.6) must be documented and graded.

6.19a Study agent is available on site

6.19b Blood draw kit is available on site.

6.19c Patient questionnaire booklet is available on site; copies are not acceptable for this submission.

6.19d At the time of randomization, the following will be verified:

- Patient has/not given permission for his/her blood sample(s) to be stored and used in future research of ovarian cancer at Mayo Clinic.
- Patient has/not given permission for his/her blood sample(s) to be stored and used in future research at Mayo Clinic to learn about, prevent, or treat any other health problems
- Patient has/not given Mayo Clinic permission to give his/her blood sample(s) to outside institutions

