7.0 Protocol Intervention

7.1 Dosing Intervention Schedule**

Agent	Dose	Route	Day	Retreat
Serum bovine immunoglobulin or placebo packets	5 grams (1-packet) per each dose*	PO	Twice a day for 12 weeks (3 cycles)	Every 4 weeks

*total dose is 10 grams per day

** Patients must begin taking agent/placebo within 7 days of registration (exceptions can be made if delays occur related to shipping agent/placebo and should be documented in the patient study record).

7.2 Patients can be instructed in administration techniques and granted intervention independence with nursing staff approval.

7.3 Patients will be instructed to add the contents of one packet (5 grams) to a cup and dissolve the powder with approximately one-half cup (4 fl. ounces, or 120 mL) of water. The patient will stir to mix and drink the contents. The patient will take one dose twice a day, in the morning and evening, with or without food.

7.4 Breaking Codes in Double-Blinded Studies-The intervention code may *not* be broken except for emergencies.

In the event of an emergency, call the MCCC Registration Office at [contact] to break the code on Monday through Friday, 8:00 a.m. to 4:30 p.m. Central Time. If the code must be broken after hours, assume the patient was assigned to active treatment and treat accordingly. Place a call to the MCCC Registration Office and leave a message informing them of the need to un-blind a patient. Provide your contact information so that MCCC Registration Office personnel can return the call the next business day.

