8.0 Dosage Modification Based on Adverse Events

There are no dose modifications in this trial. If the patient experiences a grade 1 or worse adverse event that is thought to be related to the study intervention, the patient should discontinue the intervention and proceed to the 4 week post intervention observation.

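### Section 15.16 bars breastfeeding subjects from taking SBI, but Section 3 carries over only the pregnancy half of that sentence

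*Combined protocol and SAP*

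**What the plan says.** The product information in 15.16 sets out who should not take the study product. On reproductive status it says: "Subjects who are pregnant or breastfeeding should not take SBI, as there are no data regarding the effects". On allergy it says: "Study subjects with known beef allergies or allergies to other components of SBI should not take SBI".

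Section 3 covers part of this. Criterion 3.18 begins "Negative (serum) pregnancy test done" and requires the test within 7 days before randomization. Footnote 1 of the Section 4.0 test schedule limits it: "For women of childbearing potential only". Criterion 3.24 excludes beef allergy. Breastfeeding appears nowhere in 3.11-3.19 or 3.21-3.24.

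Section 6.14 describes the control at entry: "Prior to accepting the registration, the registration/randomization application will verify the following". The list that follows is IRB approval, patient eligibility, a signed consent form and a signed authorization. Section 13.4 then defines an ineligible participant as one who, at registration, failed any of the eligibility criteria.

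**The concern.** One sentence in 15.16 names two states in which the product should not be taken, and only one of them is screened for. The entry criteria are where such a bar can be applied to every patient before randomization. If the bar sits only in the product information, it depends on someone recalling that section when the patient is registered. If nobody does, it may be noticed only after she has been randomized, or not at all.

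What is at stake is a precaution the sponsor has already adopted, and the consistency of two parts of one protocol. The trial's error rate, sample size and primary comparison are not involved.

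**Working it through.** No arithmetic beyond a count applies. The check sets the bars in 15.16 against the places where they could be enforced.

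**Step 1: from 15.16 to Section 3.**

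| State barred in 15.16 | Matching criterion in Section 3 |
|---|---|
| Pregnancy | 3.18, negative serum test |
| Breastfeeding | None |
| Beef allergy | 3.24 |
| Allergy to other components of SBI | None by name |

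**Step 2: count the criteria.** Inclusion 3.11 to 3.19 gives 9 and exclusion 3.21 to 3.24 gives 4, so 9 + 4 = 13. The number that address breastfeeding is 0 of 13. Both lists are complete in the text supplied.

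**Step 3: can 3.18 stand in for the missing criterion?** No. A pregnancy test shows whether a patient is pregnant, and a breastfeeding patient will usually test negative. The criterion also applies only to women of childbearing potential.

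**Step 4: does another step before dosing name breastfeeding?**
- Section 4.0: the only reproductive check is the pregnancy test.
- Section 6.14: the eligibility check leads back to Section 3.
- Sections 6.15 to 6.19d: these cover supervision, timing, baseline symptoms, supplies and sample permissions. None concerns breastfeeding.
- Sections 15.191 to 15.195 (nursing guidelines): 15.192 repeats the beef restriction and adds beef intolerance. Breastfeeding is not repeated.

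**Step 5: does a later step catch it?** Section 8.0 says that after a related adverse event of any grade "the patient should discontinue the intervention and proceed to the 4 week post intervention observation". That acts only once dosing has begun and an event has occurred in the patient. Under 13.4, a breastfeeding patient identified after registration would still count as eligible, because she failed no listed criterion.

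**Result.** In the supplied text the word appears once, in 15.16. A breastfeeding patient can satisfy all 13 criteria and pass the 6.14 check as described.

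**The allergy bar.** Section 15.16 goes beyond beef to other components of SBI; 3.24 does not. Section 15.12 describes SBI as immunoglobulin with other serum proteins and lists dextrose, orange flavoring and the coloring separately. The phrase most naturally means the other bovine serum proteins, and 3.24 probably covers much of that risk already. This gap is therefore secondary.

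**The case against.** The strongest reply is that the rule is already in the protocol. Section 15.16 binds staff as much as Section 3 does, and 6.15 requires the intervention to start "under the supervision of a medical oncologist". Dosing a breastfeeding patient would mean overlooking an explicit sentence. Meeting the criteria does not compel enrolment, so an investigator could decline to register her. She could also stop breastfeeding, since the bar covers only those who currently are. All of this stands. A reader might infer that the protocol permits such a patient to be dosed, or that she would necessarily be randomized. The documents support neither inference; they show only that the listed criteria and the registration check do not apply the bar.

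A second reply is that the consent form or the eligibility checklist may ask the question. The consent pages were removed and the checklist is not among the documents, so this cannot be ruled out. The point is therefore confined to the protocol text. It survives there because 13.4 judges eligibility by the criteria.

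A third reply concerns risk. Section 1.4 reports that 107 children in a trial enrolling infants under 1 year received SBI in an 8-month intervention with no related adverse events, and that 10 malnourished children aged 9 to 25 months also took it without adverse events. A reader might infer a hazard to a nursing infant from the bar in 15.16. The documents do not support that either: the reason given is lack of data. This lowers the stakes but leaves the mismatch, because the sponsor chose the precaution and moved the pregnancy and beef-allergy bars into Section 3 without this one.

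**Conclusion.** The point holds as an inconsistency between two stated rules. Section 15.16 says breastfeeding subjects should not take SBI; Section 3, as written, admits them. Confidence is high about the silence of Section 3. No claim is made about what happens in practice, which depends on pages not seen.

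The reach is very small. Maximum accrual is 100 patients (16.2), and entry requires cancer surgery more extensive than a simple hysterectomy within the previous 7 days (3.14). The documents give no rate of breastfeeding. That very few patients would be affected is a judgment from this population, not a figure in the plan.

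A reader might look for an effect on power or on the primary comparison through a patient randomized and then not dosed. The documents give no basis for sizing one, and none is claimed. This is a low-severity correction, worth making because it is nearly free.

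**What to change.** Add one exclusion criterion to 3.2, *Currently breastfeeding*, and the same item to the eligibility checklist. This applies the sponsor's own precaution before randomization.

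Optionally, extend 3.24 to read *Allergy to beef or to other components of SBI*, which follows 15.16. The wording should not be widened to any ingredient of the study product: 15.12 lists excipients that are also in the placebo, and 15.16 does not clearly extend to them. Leave 15.192 as it is. It names beef intolerance as well as allergy, and matching it to 15.16 could narrow it.

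The cost is one line in 3.2 and one on the checklist, plus a short edit to 3.24 if the option is taken, with almost no loss of accrual. No change to Section 16 is needed.

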10.6 Required Routine Reporting

Adverse events to be graded at each evaluation and preintervention symptoms/conditions to be evaluated at baseline per the CTCAE v4.0 grading unless otherwise stated in the table below:

System Organ Class (SOC)	Adverse event/Symptoms	Baseline	Each evaluation
Gastrointestinal disorders	Abdominal pain	X	X
	Bloating	X	X
	Diarrhea		X
	Baseline number of stools per day	X	
	Flatulence	X	X
	Nausea	X	X
	Vomiting	X	X
General disorders and administration site conditions	Fatigue	X	X
Infections and infestations	Wound infection	X	X
Injury, poisoning and procedural complication	Wound complication	X	X
	Wound dehiscence	X	X

10.61 Submit via appropriate MCCC Case Report Forms (i.e., paper or electronic, as applicable) the following AEs experienced by a patient and not specified in Section 10.6

10.611 Grade 2 AEs deemed *possibly, probably, or definitely* related to the study intervention or procedure.

10.612 Grade 3 and 4 AEs regardless of attribution to the study intervention or procedure.

10.613 Grade 5 AEs (Deaths)

10.6131 Any death within 30 days of the patient's last study treatment or procedure regardless of attribution to the study intervention or procedure.

10.6132 Any death more than 30 days after the patient's last study intervention or procedure that is felt to be at least possibly intervention related must also be submitted as a Grade 5 AE, with a CTCAE type and attribution assigned.

11.0 Intervention Evaluation: None**12.0 Descriptive Factors: None****13.0 Follow-up Decision at Evaluation of Participants**

- 13.1 Participants will receive 3 cycles of therapy (12 weeks) with oral SBI or placebo, followed by a 4 week observation visit. No additional follow-up is required for these patients beyond the 4 week observation time point.
- 13.2 Participants who go off the intervention early for unacceptable adverse events or patient refusal of further treatment will go to the observation phase. Patients can continue in the observation phase for total of 16 weeks of study participation.
- 13.3 Participants where post-operative problems occur, study treatment cannot begin, and participant agrees to complete questionnaires will crossover to QOL assessment only. These participants will be followed per the test schedule (Section 4.0).

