Appendix VI Nurse/CRA Phone Worksheet**Phone Contact Guide**

NOTE: This should serve only as a guide to collect information while on the phone with the patient and does not replace any data forms which are required to be filled out. Do not fill out and submit this form, rather submit the data forms using the RDE system.

1. Call patient on day 2 of cycle 1 to reinforce daily questionnaire completion and answer any questions they may have. If day 2 falls on a weekend or holiday, you may call the patient on the next business day. .
2. Call patient on day 2 of cycle 2 and day 2 of cycle 3 to assess compliance and answer questions below. Note: phone calls are only required for patients not returning to the accruing institution for monthly therapy/assessment. Patients returning to the accruing institution for monthly therapy should be seen and assessed in person. Patients not returning to the accruing institution for therapy should be assessed via phone.

1. Items to document include:

- Date of phone call.
- Study cycle.
- Compliance: Has the participant completed the questionnaire booklet each week (always, usually, rarely, never)? If not always, document reason(s) and reinforce weekly booklet completion. If never, document reason(s) in the Patient Questionnaire Booklet Compliance Form and reinforce weekly booklet completion.
- Side effects

Abdominal pain

Bloating

Diarrhea

Baseline number of stools per day

Flatulence

Nausea

Vomiting

Fatigue

Wound infection

Wound complication

Wound dehiscence

- Has the patient been taking the agent (Always or almost always; Usually; Occasionally; Rarely; Never or almost never)?

4. Reinforce compliance with booklet and remind participant to return booklet to study staff at their next appointment or in the envelope provided at the end of each 4 weeks.

5. Reinforce completion of questionnaires. NOTE: if patient decides to stop study early, ask them to fill out the questionnaires at the end of the booklet and return in the envelope provided.

7. Items to document include:

- Date of phone call.
- Study cycle.
- Patient reported weight. (lbs/kg)
- Has cancer therapy started (yes/no). If yes, chemo/RT/hormonal/other, specify-List start date of each.
- Compliance questionnaire

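### Neuropathy, constipation and headache are named SBI effects but are not routinely graded, so the adverse event profile will under-record their grade 1 and unrelated grade 2 events

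*Combined protocol and SAP*

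**What the plan says.** **Named effects.** Section 15.16 states: "Literature reports indicate AEs include worsening or reoccurrence of diarrhea, constipation, and worsening neuropathy". It goes on: "Increased urination, stomach cramps, fatigue, headache, sore throat, softened stools, and nausea have also been reported". The nursing guidelines repeat two of these. For neuropathy (15.194): "Warn of possibility of neuropathy. Instruct patients to report any development or increase in neuropathy to the study team". For headache (15.195): "Headache may occur. Treat symptomatically and monitor for effectiveness". Section 10.2 makes Section 15.0 the reference for which events count as expected.

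**Solicited events.** The Section 10.6 table is introduced as "Adverse events to be graded at each evaluation and preintervention symptoms/conditions to be evaluated at baseline per the CTCAE v4.0 grading". Its terms are abdominal pain, bloating, diarrhea (with stools per day as the baseline), flatulence, nausea, vomiting, fatigue, wound infection, wound complication and wound dehiscence. The Appendix VI phone worksheet, used for patients who do not return ("Call patient on day 2 of cycle 2 and day 2 of cycle 3 to assess compliance and answer questions below"), lists the same terms.

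**Unlisted events.** Section 10.61 covers "the following AEs experienced by a patient and not specified in Section 10.6". It requires submission at grade 2 if at least possibly related, at grade 3 and 4 whatever the attribution, and for deaths within 30 days of the last treatment (later deaths if at least possibly related).

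**Stopping.** Under Section 8.0 a patient discontinues after "a grade 1 or worse adverse event that is thought to be related to the study intervention".

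**Analysis.** Objective 2.24 is to characterize the adverse event profile. Objective 2.23 and Section 16.61 compare grade 2 or worse rates between arms. Section 16.61 also says that the maximum grade of each type of event will be recorded to 16 weeks. Neither 2.23 nor 16.61 limits the comparison by attribution.

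**The concern.** The protocol expects staff to warn patients about effects that its routine data collection does not ask about. Three consequences follow.

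- An effect described as worsening needs a starting grade. Without one, new neuropathy cannot be reliably told apart from neuropathy that was already present.
- A patient may stop the product for an event whose term, grade and attribution no stated rule requires to be submitted. Reasons for stopping are part of the tolerability picture that a later trial would want.
- The planned grade 2 or higher comparison would mix two collection rules. Listed terms are collected whatever the attribution, and unlisted terms only if judged related.

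Section 16.1 describes the trial as groundwork for a larger, definitive study. A low count for these terms could be carried forward as evidence of tolerability when part of it reflects what was not collected.

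**Working it through.** The plan states no figure on this point, so the check is a comparison of sections, followed by two small calculations.

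**1. Terms in 15.16 against the 10.6 table.**

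| Effect named in 15.16 | Solicited term in 10.6 |
|---|---|
| Diarrhea | Diarrhea |
| Softened stools | Diarrhea (nearest term) |
| Stomach cramps | Abdominal pain |
| Fatigue | Fatigue |
| Nausea | Nausea |
| Constipation | none |
| Worsening neuropathy | none |
| Headache | none |
| Increased urination | none |
| Sore throat | none |

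Five of ten map to a solicited term and five do not. The point concentrates on constipation, neuropathy and headache: neuropathy and headache are singled out again in 15.19, and constipation stands beside neuropathy in the first list of 15.16.

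**2. Required submission for these three terms, from 8.0 and 10.61.**

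| Grade | Attribution | Submission required by 10.61? | Stops product under 8.0? |
|---|---|---|---|
| 1 | related | no | yes |
| 1 | not related | no | no |
| 2 | at least possibly related | yes | yes, if thought related |
| 2 | unlikely or unrelated | no | no |
| 3–4 | any | yes | yes, if thought related |

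The first row is the mismatch between 8.0 and 10.61. Expedited reporting in 10.4 does not close it, because a grade 1 event without hospitalization of at least 24 hours needs no expedited report. The fourth row is the mismatch between 10.611 and 2.23/16.61.

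**3. What a zero count would show.** By the rule of three, the upper 95% bound on a rate after zero events in n patients is about 3/n. Section 16.2 gives 35 evaluable and at most 50 accrued per arm:

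- n = 35: 3/35 = 8.6%
- n = 50: 3/50 = 6.0%

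For an unlisted term this bound applies to reportable events only: related grade 2, any grade 3–4, and reportable deaths. It says nothing about grade 1 events or grade 2 events judged unrelated.

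**4. How often the 8.0/10.61 mismatch might matter.** The documents give no rate for unlisted related grade 1 events, so an assumed range is used. With 35 SBI patients, the expected number is 35p and the chance of at least one is 1 − (1 − p)^35.

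| Assumed p | Expected patients | Chance of at least one |
|---|---|---|
| 2% | 35 × 0.02 = 0.7 | 1 − 0.98^35 = 51% |
| 5% | 35 × 0.05 = 1.75 | 1 − 0.95^35 = 83% |
| 10% | 35 × 0.10 = 3.5 | 1 − 0.90^35 = 98% |

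The number of patients is small, but at least one such case is more likely than not across this range.

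**The case against.** A short solicited list with a threshold for everything else is an ordinary design choice in a pilot, and several features soften the gap.

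- **Reportable events.** A reader might infer that the safety profile misses these effects altogether. It does not: all three terms must be submitted at grade 2 if even possibly related, and at grade 3–4 regardless. Patients are told to report neuropathy, and 15.191 asks staff to watch closely for side effects. What stands is under-recording below those thresholds. A neuropathy report that is graded 1 still need not be submitted.
- **Listed terms.** A reader might also infer that no grade 1 event that stops treatment need be reported. That is true only outside the 10.6 table; listed terms are graded from grade 1 at every evaluation.
- **Constipation.** The booklet asks at baseline and weekly about bowel frequency, stool form and closeness of bowel function to normal, and the Symptom Distress Scale has a bowel item. Section 16.63 compares the Postoperative Quality of Life items and the four added items between arms. A change in bowel habit can therefore be seen, though not as a graded adverse event. No booklet item asks about neuropathy or headache.
- **End-of-intervention forms.** Section 18.12 requires an Adverse Event Form and an End of Active Intervention form. Their fields are not shown, so they may capture the reason for stopping. They cannot be assumed to do so.
- **Appendix VI.** It describes itself as a guide that does not replace data forms, so its omissions weigh less than those in 10.6.
- **Severity of the effects.** It would be tempting to say that these effects are mostly low grade. Section 15.16 gives no grades or rates for them. Difficulty of attribution once chemotherapy starts is plausible, but it is an inference and the point does not depend on it.

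**Conclusion.** The point holds in a limited form. Following the plan as written, objective 2.24 will under-record grade 1 events, and grade 2 events judged unrelated, for three effects that the protocol itself names. It will have no baseline CTCAE grade for any of them, which matters most for worsening neuropathy. An unlisted related grade 1 event stops the product but falls below the submission threshold. The comparison in 2.23 and 16.61 asks for grade 2 events that 10.611 does not require for unlisted terms.

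A reader might conclude that a zero count would bound nothing. That goes too far: it would still bound the reportable events at about 6% (50 per arm) to 9% (35 per arm). It would not bound all-grade rates.

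The conclusion assumes that the forms collect what 10.6 and 10.61 require and no more. If the end-of-intervention form already records the term, grade and attribution of the event behind a stop, that part of the concern falls away. The primary endpoint is unaffected, and so is the grade 3 or worse accrual rule in 16.52. This is a cheap improvement to two secondary safety objectives, not a flaw in the main design.

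**What to change.** 1. Add neuropathy, constipation and headache to the Section 10.6 table, at baseline and each evaluation, and to the Appendix VI list.
2. In Section 10.61, require submission, with term, grade and attribution, of any adverse event that leads to discontinuation of the product, whatever its grade.
3. Reconcile 10.611 with 2.23 and 16.61: either collect grade 2 events regardless of attribution, or limit the stated comparison to the events that are collected.

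The stopping rule in Section 8.0 is not changed; only the data recorded when it is applied are.

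The cost is three more rows at each adverse event assessment. Section 4.0 schedules five (baseline, day 1 of cycles 2 and 3, end of intervention, observation), so at most 3 × 5 = 15 extra grades per patient. To this add one sentence in 10.61 and slightly more data entry, with a further increase if item 3 is met by wider grade 2 collection. No new visits or staff are needed.
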